7.9.3 Secondary Objective #2 – NOSE at the 6-Month Visit

To characterize the change in opioid-related side effects scores (NOSE) from Baseline to the 6-Month Visit.

7.9.3.1 Hypothesis

There is no formal hypothesis. The objective is to estimate the change in NOSE from Baseline to the 6-Month Visit.

7.9.3.2 Experimental Design

The measurement of opioid-related side effect using NOSE is described in Section 5.2.1.2. The total NOSE score is the sum of each score from the 10 opioid-related side effects normalized by the number of scores provided. The change in NOSE is calculated using total NOSE score at the 6-Month Visit minus the total NOSE score at Baseline. A negative change is an improvement.

7.9.3.3 Analysis Methods

The change in NOSE as well as the total NOSE score at Baseline and the 6-Month Visit will be summarized using descriptive statistics (e.g., mean, standard deviations, etc.). The analysis will use all the implanted subjects who maintain morphine monotherapy and provide data at both Baseline and the 6-Month Visits.

Two sensitivity analyses will be performed, one will include subjects who provide data (completers) and one will include all implanted subjects. The sensitivity analysis of all implanted subjects will be

performed using MI method for missing data at the Baseline and the 6-Month Visits. For missing NOSE at the scheduled 6-Month Visit, if an Unscheduled Visit occurred within the 6-Month Visit window, and NOSE is collected at the Unscheduled Visit, the NOSE from the Unscheduled Visit will be used in the analysis of the 6-Month Visit. Otherwise, the missing NOSE will be imputed using MI. Prior to the use of MI, the distributions of the continuous variables will be assessed for normality and the need for transformation if they are not normally distributed. The model variables in MI may include the following when deemed appropriate: study site, subject age, gender, primary diagnosis, NOSE at Baseline, 1-Month Visit, 3-Month Visit. The fully conditional specification method with 10 burn-in iterations within SAS and 10 repetitions ($M = 10$) will be used for imputation. Constraints will be set so that the imputed NOSE are restricted to values ranging from 0-100. If the MI procedure is unable to successfully impute values within that range, the constraints will be applied after imputation, such that any values less than 0 will be set to 0, and any values greater than 100 will be set to 100. Following imputation, the objective will be evaluated using MI analysis method.

In addition, percentage of change in NOSE will be calculated using change in NOSE divided by the total NOSE score at Baseline. A negative percentage of change in NOSE is a percentage of reduction in NOSE, thus an improvement. The percentage of change in NOSE will be summarized using descriptive statistics, (e.g., median and inter-quartile range, etc.). If a subject has NOSE equal to 0 at both the Baseline and the 6-Month Visit, the percentage of change will be 0%. If a subject has NOSE equal to 0 at the Baseline visit, and non-zero at the 6-Month Visit, this subject will be excluded from summary of percentage of change in NOSE.

NOSE score for each individual opioid-related side effect at Baseline and 6-Month Visit will be summarized using descriptive statistics (e.g., mean, standard deviations, etc.).

If more than 10% of the 6-Month Visits within the Per-protocol Analysis Set are conducted remotely, an additional sensitivity analysis of the Per-protocol Analysis Set will be performed as described in Section 7.4.1.

7.9.4 Secondary Objective #3 – Systemic Opioids Elimination through the 6-Month Visit

To characterize the proportion of subjects who eliminate systemic opioids through the 6-Month Visit.

7.9.4.1 Hypothesis

There is no formal hypothesis. The objective is to estimate the proportion of subjects who eliminate systemic opioids through the 6-Month Visit.

7.9.4.2 Experimental Design

The test for systemic opioids and illicit drug use will be collected at all scheduled study visits except for the Implant Visit and Post-op Visit. If a subject has a negative test for systemic opioid use, this subject will be considered as having eliminated systemic opioids at the scheduled study visit.

[figure not shown]

A series of 10 horizontal black bars of varying lengths, each with a small white rectangular notch on its left side. The bars are arranged vertically, with the notch on the first bar pointing upwards and the notch on the last bar pointing downwards.

This image consists of a large, solid black rectangular area. It features several white rectangular highlights: one at the top center, one on the left side, and a larger one on the right side. There are also small white marks on the left side, including a short vertical line and a horizontal line above it. The overall appearance is like a high-contrast scan of a physical object or a specific frame from a video.

7.10 Safety Evaluation

The safety evaluation will characterize all systemic opioid weaning-related, device-related, IT drug-related, and procedure-related adverse events (AEs), all serious adverse events (SAEs) (regardless of relatedness), and device deficiencies (DD) for all subjects from enrollment until the subject exits.

Adverse events and device deficiencies will be coded and summarized using the most recent version of Medical Dictionary for Regulatory Affairs (MedDRA).

The adverse events will also be categorized by relationship to systemic opioid weaning-related, device-related, IT drug-related, and procedure-related adverse events. The CEC adjudicated relatedness will be used for summary tables in the final report. Any differences between CEC adjudication and investigator reporting will be noted in the final report.

Adverse events will be presented in summary tables displaying the number of serious events, the number of events, and the number and percentage of subjects with one or more events. A summary of all adverse events by System Organ Class (SOC) and Preferred Term (PT) will also be provided.

Device deficiencies will be presented in summary tables displaying the number of deficiencies, and the number and percentage of subjects with device deficiencies.

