Change from Baseline to the 6-Month Visit			Opioid-Related Side Effects (NOSE)																																	
Pain Intensity (VAS)	≥20% Increase	Worse	≥20% Increase	< ±20% Change	≥20% Reduction																															
	Worse	Equal	Better	Worse	Equal	Better																														
	≥20% Reduction	Better	Worse	Worse	Equal	Better																														
1	2	3	Worse	Equal	Better																															
Secondary Objectives	
 1. To demonstrate pain intensity scores (VAS) at the 6-Month Visit is non-inferior to VAS at Baseline 2. To characterize the change in opioid-related side effect scores (NOSE) from Baseline to the 6-Month Visit 3. To characterize the proportion of subjects who eliminate systemic opioids through the 6-Month Visit 																																			

Embrace TDD Clinical Investigation Plan

MDT18026

Version 3.0

Page 11 of 74

Form

Medtronic

Safety Assessments	To characterize all systemic opioid weaning-related, device-related, IT drug-related, and procedure-related adverse events (AEs), all serious adverse events (SAEs) (regardless of relatedness), and device deficiencies (DD) for all subjects from enrollment until the subject exits.
Study Design	The Embrace TDD study is a prospective, multi-center, post-market study. Subjects with chronic, intractable non-malignant primary back pain with or without leg pain will be enrolled in the study and will be required to attend a minimum of 7 in-office visits which include: Baseline, Intrathecal Trial, Implant, Post-Op, 1-Month, 3-Month, and 6-Month. Participation in the study can last up to 18 months for a subject depending on weaning duration and follow-up requirements in place prior to CIP V3.0 implementation.
Sample Size	93 subjects have been enrolled into the study with the intent to achieve approximately 67 implanted subjects and 50 evaluable subjects at the 6-Month Visit. The sample size of 50 evaluable subjects was chosen to assure acceptable levels of precision for estimation of the primary objective of Clinical Success and provide adequate power to test the secondary objective related to pain score.

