12.1 Definitions / Classifications

Any adverse event (AE) meeting the definition of systemic opioid weaning-related, device-related, IT drug-related, and procedure-related, all serious adverse events and deaths (regardless of relatedness) for all subjects from Baseline to the 6-Month Visit, and device deficiencies (DD) for all subjects from Implant to the 6-Month Visit will be collected. All anticipated AEs and adverse device effects are the same as those foreseeable risks listed in Section 11.1.

This post-market study is not within the scope of ISO 14155:2011 but will use AE definitions according to ISO 14155:2011 for consistency in reporting. Each adverse event is classified according to ISO 14155:2011. Adverse events and device deficiencies are defined below in Table 4 as follows:

Table 4: Adverse Event and Device Deficiency Definitions

Term	Definition
Adverse Event (AE): (ISO 14155:2011 3.2)	Any untoward medical occurrence, unintended disease or injury, or untoward clinical signs (including abnormal laboratory findings) in subjects,

Embrace TDD Clinical Investigation Plan

MDT18026

Version 3.0

Page 51 of 74

Form

Medtronic

Term	Definition
	
users or other persons, whether or not related to the investigational medical device.
 
NOTE 1: This definition includes events related to the investigational medical device or the comparator.
 
NOTE 2: This definition includes events related to the procedures involved.
 
NOTE 3: For users or other persons, this definition is restricted to events related to investigational medical devices.

Adverse Device Effect (ADE): (ISO 14155:2011 3.1)	
Adverse event related to the use of an investigational medical device.
 
NOTE 1: This definition includes adverse events resulting from insufficient or inadequate instructions for use, deployment, implantation, installation, or operation, or any malfunction of the investigational medical device.
 
NOTE 2: This definition includes any event resulting from use error or from intentional misuse of the investigational medical device.

Device Deficiency (DD): (ISO 14155:2011 3.15)	
Inadequacy of a medical device with respect to its identity, quality, durability, reliability, safety or performance.
 
NOTE: Device deficiencies include malfunctions, use errors, and inadequate labeling.

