2.0	
Transferred content to new template (vB)Updated non-inferiority margin for Secondary Objective #1 to 10 from 1Added considerations due to COVID-19, including:
Exits and deviationsData handling of remote visits[REDACTED]Updated primary analysis for primary objectiveAdded explanation of differing follow-up duration for CIP v3Added analysis clarifications and minor edits throughout	[REDACTED] Principal Statistician

2. List of Abbreviations and Definitions of Terms

Abbreviation	Definition
AE	Adverse Event
ATC	Anatomical Therapeutic Chemical
[REDACTED]	[REDACTED]
CI	Confidence Interval
CIP	Clinical Investigational Plan
COVID-19	Coronavirus Disease 2019
DD	Device Deficiency
[REDACTED]	[REDACTED]
FCS	Fully Conditional Specification
IDDS	Intrathecal Drug Delivery System
IT	Intrathecal
MedDRA	Medical Dictionary for Regulatory Affairs
MI	Multiple Imputation
MME	Morphine Milligram Equivalents
NOSE	Numerical Opioid Side Effect
[REDACTED]	[REDACTED]
PFMS	Preservative-Free Morphine Sulfate
[REDACTED]	[REDACTED]

Abbreviation	Definition
AE	Adverse Event
PT	Preferred Term
SAE	Serious Adverse Event
SAP	Statistical Analysis Plan
SAS	Statistical Analysis Software
SOC	System Organ Class
[REDACTED]	[REDACTED]
TDD	Target Drug Delivery
VAS	Visual Analog Scale
WHO	World Health Organization

3. Introduction

This statistical analysis plan (SAP) is based on Version 3 of the Embrace TDD Study Clinical Investigational Plan (CIP). CIP v3.0 changed the last study visit from the 12-Month Visit to the 6-Month Visit. Some subjects will have follow-up in the study past the 6-Month Visit, and other subjects will not have follow-up through the 12-Month Visit due to being consented and exited under CIP v3.0. The SAP presents the details of the methods to be used to analyze and report the study results of the Embrace TDD study, protocol number MDT18026.

4. Study Objectives

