5.2.3 Schedule of Events by Visit and Visit Windows

Study procedures and data collection requirements for the study are summarized in Table 5-1. The study visit windows for all the required study visits are provided in Table 5-2. The 9- and 12-Month Visits were required under CIP v1.0 and v2.0; they are not scheduled study visits under CIP v3.0.

Table 5-1 Schedule of Events by Visit

Study Procedures, Tasks, and Data Collection (row) by Visit (column)	Baseline Visit (Enrollment)	Intrathecal Trial Visit		Implant Visit	Post-Op Visit	IT Therapy Initiation	1-Month Visit	3-Month Visit	6-Month Visit	9-Month Visit ¹	12-Month Visit ¹	Unscheduled Visits
		IT	Implant									
Informed Consent Process	✓											
Demographics	✓											
Inclusion/Exclusion Criteria	✓	✓										
Urine Pregnancy Test	✓	✓	✓ ²			✓	✓	✓	✓	✓	✓	
Drug Test	✓	✓				✓	✓	✓	✓	✓	✓	
Adjunctive pain management therapies	✓	✓	✓			✓						
Back and Leg Pain/Surgical History	✓											
VAS	✓	✓				✓	✓	✓	✓	✓	✓	
NOSE Assessment	✓	✓				✓	✓	✓	✓	✓	✓	
IT PFMS Dose						✓	✓	✓	✓	✓	✓	
Fluoroscopy/x-ray			✓									
Device information (model, serial/lot #)			✓									
Drug information (name, lot #/identifier, dose & concentration)		✓				✓	✓	✓	✓	✓	✓	
Initial and final device interrogation reports			✓	✓	✓	✓	✓	✓	✓	✓	✓	
Collect AEs/DDs	✓ ³	✓	✓ ³	✓	✓	✓	✓	✓	✓	✓	✓	
Pain Medications	✓	✓	✓	✓	✓	✓	✓	✓	✓	✓	✓	

¹Required visits under CIP v1.0 and v2.0, not required under CIP v3.0.

²Confirm pregnancy test completed within 2 weeks prior to implant visit

³Device Deficiencies will be collected and reported from the Implant Visit through the 12-Month Visit/Study Exit

Table 5-2 Visit Windows

Study Visits	Visit Windows	
Baseline Visit	Date of Enrollment (Date ICF/HIPAA signed and dated)	
Intrathecal Trial Visit	After Baseline and prior to Implant	
IT Therapy Initiation (Day 0) Implant to Post-Op Visit	Implant Visit	≤150 days after the Baseline Visit
	Post-Op Visit	14 ± 4 days after the Implant Visit
	1-Month Visit	30 days ± 5 days after Day 0
	3-Month Visit	90 days ± 10 days after Day 0
	6-Month Visit ¹	180 days ± 10 days after Day 0
	9-Month Visit ²	270 days ± 15 days after Day 0
	12-Month Visit (Study Exit) ²	360 days ± 15 days after Day 0

¹ Study Exit Visit under CIP v3.0² Required Visits under CIP v1.0 and 2.0

[figure not shown]
6. Determination of Sample Size

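### Adverse-event and device-deficiency percentages in SAP 7.10 run to each subject's own exit, which CIP v3.0 places anywhere from the 6-Month to the 12-Month Visit, so they are neither a 6-month nor a 12-month risk

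*SAP*

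**What the plan says.** SAP 7.10 (Safety Evaluation) covers weaning-, device-, IT-drug- and procedure-related adverse events, all serious adverse events and device deficiencies "for all subjects from enrollment until the subject exits". The adverse-event tables are described as "displaying the number of serious events, the number of events, and the number and percentage of subjects with one or more events". Device deficiencies get the same kind of summary: a count, and the number and percentage of subjects affected. No text in 7.10 is visibly redacted.

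Follow-up length differs by protocol version:

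- SAP section 3: "Some subjects will have follow-up in the study past the 6-Month Visit, and other subjects will not have follow-up through the 12-Month Visit", because of consent and exit under CIP v3.0.
- SAP 5.2.3: "The 9- and 12-Month Visits were required under CIP v1.0 and v2.0; they are not scheduled study visits under CIP v3.0". Exit is at "180 days ± 10 days after Day 0" under v3.0 and at "360 days ± 15 days after Day 0" under the earlier versions.
- Protocol 10.10: subjects who have already completed the 6-Month Visit are brought in, re-consented and exited.
- Protocol synopsis, Study Design: "Participation in the study can last up to 18 months for a subject depending on weaning duration and follow-up requirements in place prior to CIP" (the sentence goes on to name the third version).

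The collection windows are not worded alike. For adverse events, Protocol 12.1 has "for all subjects from Baseline to the 6-Month Visit", while Protocol 5.1.4, 12.2 and 14.6 run to study exit, as the SAP does. For device deficiencies, Protocol 12.1 and 12.4 end at the 6-Month Visit, while footnote 3 of SAP Table 5-1 ends at the 12-Month Visit/Study Exit.

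SAP 7.7 defines exposure to IT therapy, but 7.10 does not use it.

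**The concern.** A crude percentage of subjects with an event can be read as a risk only if the observation time is roughly common to all subjects or is accounted for. Here it is neither. One subject may leave at about 180 days after Day 0, another at about 360 days, and others in between, according to where they stood when v3.0 was implemented at their site. Two studies with identical patients and identical devices would report different percentages if the amendment had come earlier or later.

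Safety is a stated objective for an implanted system, and Protocol 16.9 foresees publication. All the primary and secondary efficacy objectives are fixed at or through the 6-Month Visit. The safety percentages have no matching time point, so benefit and risk would be shown side by side over different periods.

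**Working it through.** The documents give no safety figure to reproduce. The durations can be checked, because they set the follow-up ratio.

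**Follow-up clock.** The SAP 7.10 window starts at enrollment, not at Day 0.
- To the 6-Month Visit: up to 150 days to implant, 14 days to the Post-Op Visit if therapy starts there, then 180 days. That is 150 + 14 + 180 = 344 days, or 344/30.4 = 11.3 months, in line with the roughly 11 months in Protocol 6.1.
- To the 12-Month Visit: 180 days (about 6 months) more, so about 17 months. The outer limit is 150 + 18 + 375 = 543 days, or 17.9 months, in line with the synopsis maximum of 18 months.
- Ratio of follow-up: 17/11 = 1.55.

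**Mixture.** Let R6 be the risk to the 6-Month Visit, R12 the risk to the 12-Month Visit, and f the share followed to 12 months, with all others followed to 6 months. Then

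pooled percentage = (1 − f) × R6 + f × R12.

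This equals R6 only if f = 0 and R12 only if f = 1. SAP section 3 says both kinds of subject exist, so under this simplification the reported figure lies strictly between the two risks whenever R12 exceeds R6.

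**Illustration.** R6 = 30% and f = 30%, 50%, 70% are assumptions; the documents give neither.

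Constant hazard from enrollment: R12 = 1 − (1 − 0.30)^1.55 = 42.4%.

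| f | Calculation | Pooled |
|---|---|---|
| 30% | 0.70 × 30 + 0.30 × 42.4 | 33.7% |
| 50% | 0.50 × 30 + 0.50 × 42.4 | 36.2% |
| 70% | 0.30 × 30 + 0.70 × 42.4 | 38.7% |

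Front-loaded events, with 80% of the cumulative hazard before the 6-Month Visit: R12 = 1 − (1 − 0.30)^(1/0.80) = 1 − 0.70^1.25 = 36.0%. The pooled values are 31.8%, 33.0% and 34.2%.

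**Plausible range of f.** With 93 enrolled, f = 70% means about 65 subjects followed to 12 months, nearly all of the 67 expected to be implanted. That is not realistic for an all-enrolled table; it is conceivable only with the Implanted Analysis Set as denominator.

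**Which events are affected.** Weaning, IT-trial and implant-procedure events occur mostly before or soon after Day 0, so extra months add little. Catheter, pump and IT-drug events can only accrue once the system or drug is in place and continue to accrue, so extra months matter more.

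**The case against.** The best defence is that the plan does state a period, enrollment to exit, and states it consistently in SAP 4.4 and 7.10 and Protocol 5.1.4 and 14.6. The safety objective is descriptive, in a single-arm study with no safety hypothesis. The SAP never labels the percentage a 6-month or 12-month risk, it discloses the unequal follow-up, and a complete record of all events to exit is a legitimate safety display. No data are lost, since a split table can be made later from the same dates.

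Most of this stands, and it rules out several stronger readings that a reader might infer:

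- *That no follow-up period is defined.* One is defined; its length varies by subject.
- *That the SAP contradicts the protocol on adverse events.* Protocol 12.2 agrees with the SAP. The difference lies mainly within the protocol, between 12.1 and 12.2, and disappears for subjects whose exit is the 6-Month Visit.
- *That follow-up doubles.* Counting from Day 0 gives R12 = 1 − 0.70² = 51% and pooled values of about 36%, 41% and 45%. The table's window starts at enrollment, so the protocol's own durations give a ratio of about 1.55. It would approach two only if the time before Day 0 were negligible.
- *That the reported figure must exceed the 6-month risk.* Early withdrawals, and never-implanted subjects in the Full Analysis Set, pull the other way.
- *That the results cannot be compared with other studies.* The documents give no other study's adverse-event window, so this cannot be judged from them.

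What the defence does not answer is that disclosing unequal follow-up in section 3 leaves the percentages in 7.10 uncorrected for it, and that readers of a percentage will attach a time to it.

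**Conclusion.** The point holds as a matter of interpretation. The SAP 7.10 percentages for adverse events and device deficiencies depend partly on amendment timing and estimate neither a 6-month nor a 12-month risk. The size is unknown, because the documents give neither the number followed past 6 months nor any event rate. Under an assumed 30% risk to the 6-Month Visit, the pooled figure is about 34% to 39% with constant hazard from enrollment and 30% to 70% followed to 12 months. It is about 32% to 34% if events are front-loaded. These are illustrations, not estimates, and the upper end is implausible for the all-enrolled table. Device and IT-drug events that accrue over time are the ones to watch. The efficacy objectives are not affected.

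**What to change.** In SAP 7.10:

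1. Add adverse-event, serious-adverse-event and device-deficiency tables limited to events through the 6-Month Visit, or earlier exit, and make these the headline percentages. Use the Implanted Analysis Set for device-, IT-drug- and procedure-related events and for device deficiencies, as SAP 7.1.3 already foresees.
2. Keep the all-events-to-exit tables as the complete record.
3. Report events after the 6-Month Visit separately, per patient-year, counting only person-time after that visit. The exposure in SAP 7.7 runs from IT Therapy Initiation, so using it here would add the first six months to the denominator and understate the rate. Alternatively, give cumulative incidence at 6 and 12 months with a stated time origin. This assumes that exit caused by the amendment is unrelated to event risk.
4. Reconcile the collection windows in Protocol 12.1, 12.2 and 12.4 and footnote 3 of SAP Table 5-1.

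The first step does not give a strictly fixed-period risk, since time to implant varies up to 150 days and some subjects exit early. It does remove the dependence on the amendment. Cumulative incidence would also deal with early exit. The cost is SAP wording and one extra set of tables from dates already collected.

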7.11 Changes to Planned Analysis

The main analysis for the primary objective was originally planned to be evaluated after all subjects had reached the 6-Month Visit. The primary analysis was changed to analyze all per-protocol subjects with a 6-Month Visit through the snapshot date in November 2021 (Primary Objective Analysis Set, which will be a subset of the Per-Protocol Analysis Set). The primary objective is a characterization of the clinical success rate; it is a descriptive analysis with no hypothesis testing. Therefore, this change will affect the precision around the estimated clinical success rate for the main analysis but will otherwise minimally impact the objective. Additionally, all subjects within the Per-Protocol Analysis Set who eventually complete the 6-Month Visit will be evaluated as a sensitivity analysis for the primary objective to assess the robustness of the results.

8. Validation Requirements

Statistical programming code that affects the result of the main analysis for the primary objective shall be validated using Level I validation, which is defined as the peer reviewer independently programs output and then compares the output with that generated by the original Statistical Programmer.

Statistical programming code that affects the result of the main analysis for the secondary objectives shall be validated using at least Level II validation, which is defined as the peer reviewer reviews the code, and where appropriate, performs manual calculations or simple programming checks to verify the output. The CIP deviation summary shall be validated using at least Level III validation and the high-level adverse event summary shall be validated using at least Level II validation.

In addition, the main statistical analyses that are planned for publication and have not been previously validated should be validated with at least Level II validation.

9. References

[REDACTED]
2. [REDACTED]
3. [REDACTED]
4. NOSE: Smith HS, Kirsh KL. Documentation and potential tools in long-term opioid therapy for pain. *Anesthesiol Clin.* 2007 Dec;25(4):809-23, vii.
[REDACTED]
5. [REDACTED]
6. [REDACTED]
7. [REDACTED]
